If at an Evaluation for Re-treatment visit the subject wants to get re-treated, but the investigator does not agree or vice versa (i.e. the FWS score is not ≥ 2 by both assessments), the subject will return to the site 4 weeks thereafter for another Evaluation for Re-treatment visit. There is no limit to the number of Evaluation for Re-treatment visits. In order to consider a visit as the End of Cycle visit, there must always be agreement between investigator and subject on a FWS score (at maximum frown) of ≥ 2 .

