7.3 Eligibility Criteria for Re-treatment

The following criteria **MUST** be met for re-treatment:

- At time of re-treatment subject does not have relevant changes to their health status from enrollment, which would have prevented subject's entry into the study according to the inclusion and exclusion criteria.
- The subject must have been randomized to receive treatment and must have received at least one treatment (BoNT/A-DP or placebo).
- A minimum of 12 weeks must have elapsed since the previous study treatment.
- The subject's glabellar lines at maximum frown must have relapsed to a FWS score of 2 or 3 as determined by both the investigator and the subject.
- No relevant infection or inflammation in the planned injection area.
- Negative urine pregnancy test, in women of child-bearing potential.
- The subject must have received fewer than four study treatments.
- The subject must agree and consent to re-treatment.
- Re-treatment will be performed at the latest by week 48.

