In general, the additional secondary efficacy endpoints will be analyzed applying the appropriate statistical method for the comparison of both treatment arms. For proportions, the Cochran-Mantel-Haenszel test (with stratification variable site) and the Pearson χ^2 -test will be applied. In case of a total number of observations below 30, or in case of at least one cell frequency below 5, Fisher's exact test will be used instead of the χ^2 -test. Two-sided 95% CIs for response rates will be calculated, where appropriate. Additionally the cumulative proportions of effects at weeks 1, 2, and 4 will be calculated. Time to onset of effect in the first treatment cycle will be analyzed descriptively and by using the Kaplan-Meier method. Moreover, the daily assessments of the line severity when frowning will be analyzed descriptively. The FACE-Q satisfaction with outcome scale will be analyzed descriptively.

All endpoints, with exception of "responder" 4 weeks after re-treatment, will be analyzed for the first treatment cycle only. The analysis of "responder" 4 weeks after re-treatment will be conducted on observed values only, i.e. subjects with missing investigator or the subject inclinic assessments on FWS week 4 or at the preceding end of the cycle visit will be excluded from analysis. Subjects who were treated with placebo during the first treatment cycle are excluded from the analysis of this endpoint, but not assigned as being non-responders. A two-sided McNemar test (using a significance level of 0.05) will be used to compare the response

proportions between week 4 re-treatment visit and at the preceding end of the cycle visit. This endpoint will be separately analyzed for each open label extension cycle.

Analyses of percentage of responders at other visits after first treatment but before retreatment are exploratory only. Additional exploratory analyses, as described for the primary endpoint, will not be conducted, with the exception of the calculation of 95% Cls.

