If at an Evaluation for Re-treatment visit the subject wants to get re-treated, but the investigator does not agree or vice versa (i.e., the FWS score is not \geq at least 2 by both assessments), the subject will return to the site four weeks thereafter for another Evaluation for Re-treatment visit. There is no limit to the number of Evaluation for Re-treatment visits. In order to consider a visit as the End of Cycle visit, there must always be agreement between investigator and subject on a FWS score (at maximum frown) of ≥ 2 .

End of Study Visit

The End of Study visit can take place in four-weekly intervals from study-week 48 until study-week 60. The last study drug re-treatment will be administered no later than week 48. For subjects receiving a re-treatment at week 48, the last cycle will end 12 weeks later at week 60 (i.e., End of Study visit).

The End of Study visit will take place at week 48 if the week 48 visit is an Evaluation for Re-treatment visit and the subject does not meet the criteria for re-treatment in case this visit is 12 or more weeks after the last treatment. As week 48 is the last possible time point for re-treatment, such subjects will continue with all additional assessments of the End of Study visit on the same day. For subjects having received their last injection eight weeks or less prior to week 48, the End of Study visit will take place 12 weeks after the last study drug treatment was given, e.g. week 52 if the subject was re-treated at week 40.

For subjects who are prematurely discontinued from the study (at any time), the End of Study visit will take place within one week of discontinuation.

A detailed description of procedures and assessments to be conducted during this study is summarized in the Scheduled of Study Assessments in Table 1 below.

COVID-19 Pandemic

Due to the COVID-19 pandemic, which touched the world mainly the first 6 months of 2020, it has been allowed that visits were done remotely instead of physically when site was closed.

All re-treatments were put on hold between the 16th March and 5th May 2020 due to concerns that the subject will not be able to return for Week 1 and Week 4 assessments. Consequently, when a subject was eligible for re-treatment at a visit, the injection has been delayed until the subject could go back to site (if the injection is done before or at Week 48).

	Statistical Analysis Plan (SAP)	croma est. 1976
---	--	---------------------------

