11. The percentage of subjects with a FWS score of 0 or 1 and an improvement of ≥ 2 points in FWS score at maximum frown (investigator and subject assessment) at four weeks after re-treatment relative to the rating at the preceding end of cycle visit.
12. The proportion of subjects with ≥ 1 point reduction in FWS score (at maximum frown) in the BoNT/A-DP and placebo groups during the first treatment cycle at weeks 1, 2, 4, 8, 12, 16 and 20 relative to baseline, based on both the investigators' and the subjects' in-clinic assessments.
13. The proportion of subjects with ≥ 1 point reduction in FWS score (at maximum frown) in the BoNT/A-DP group during each re-treatment cycle at week 4 relative to re-treatment-baseline, based on both the investigators' and the subjects' in-clinic assessments.

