- of subjects with an improvement of ≥ 2 points in FWS at maximum frown at 4 weeks after re-treatment,
- of subjects with ≥ 1 point reduction in FWS score at maximum frown (at weeks 1, 2, 4, 8, 12, 16 and 20 relative to baseline,
- of subjects with ≥ 1 point reduction in FWS score at maximum frown at week 4 relative to re-treatment baseline,

the CMH test (with stratification variable site) and the Pearson χ^2 -test will be applied. In case of a total number of observations below 30, or in case of at least one cell frequency below 5, Fisher's exact test will be used instead of the χ^2 -test. Two-sided 95% CIs for response rates will be calculated, where appropriate. Additionally, the cumulative proportions of effects at weeks 1, 2, and 4 will be calculated.

Time to onset of effect in the first treatment cycle will be analyzed descriptively and by using the Kaplan-Meier method. Moreover, the daily assessments of the line severity when frowning will be analyzed descriptively. The FACE-Q satisfaction with outcome scale will be analyzed descriptively.

All efficacy endpoints, with the exception of “responder” 4 weeks after re-treatment, will be analyzed for the first treatment cycle only. The analysis of “responder” 4 weeks after re-treatment will be conducted on observed values only, i.e., subjects with missing investigator or the subject in-clinic assessments on FWS week 4 or at the preceding end of the cycle visit will be excluded from analysis. Subjects who were treated with placebo during the first treatment cycle are excluded from the analysis of this endpoint, but not assigned as being non-responders. A two-sided McNemar test (using a significance level of 0.05) will be used to compare the response proportions between week 4 re-treatment visit and at the preceding end of the cycle visit. These endpoints will be separately analyzed for each open label extension cycle.

In addition to the FAS population, the analyses of these endpoints will also be based on the MFAS and PP populations. For all analyses, a one-sided significance level of 0.025 will be used, if not stated otherwise. Additional exploratory subgroup analyses will be conducted as described in Section 8.8.

Statistical Analysis Plan (SAP)

CROMA
est. 1976

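### The McNemar test after re-treatment compares week-4 response with a visit where response is zero by design, so it cannot show whether efficacy is maintained across cycles

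*SAP*

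**What the plan says.** Endpoint 11 (SAP 4.3) counts subjects with "FWS score of 0 or 1 and an improvement of ≥ 2 points in FWS score at maximum frown", by investigator and subject, four weeks after "re-treatment relative to the rating at the preceding end of cycle visit".

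For this endpoint, Protocol 12.4.2 states: "A two-sided McNemar test (using a significance level of 0.05) will be used". SAP 8.1 and 8.6.4 repeat this. The purpose given is to "compare the response proportions between week 4 re-treatment visit and at the preceding end of the cycle visit", separately in each open-label cycle.

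The End of Cycle visit has its own entry rule. Protocol 6.3.2 says: "In order to consider a visit as the End of Cycle visit, there must always be agreement between investigator and subject on a FWS score" of at least 2 at maximum frown, and SAP 3.3 agrees. Protocol 7.3 adds, for re-treatment, that the lines "must have relapsed to a FWS score of 2 or 3 as determined by both the investigator and the subject".

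SAP 8.6.4 also lists endpoint 11 and endpoint 13 (a reduction of at least 1 point at week 4 from the re-treatment baseline) among the proportions to be compared between both treatment arms by CMH and chi-square tests. It then says: "Subjects who were treated with placebo during the first treatment cycle are excluded from the analysis of this endpoint".

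SAP 8.6.1.1 classes all additional secondary analyses as exploratory. SAP 8.6.4 plans 95% confidence intervals for response rates, but only where appropriate.

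**The concern.** A before-after test is informative only if the before value could have been something else. Here the rule that opens a new cycle requires the subject to be a non-responder, so the comparison value is set by the visit rules and not by the drug.

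Efficacy after repeat treatment is part of the study purpose (Protocol 5.1), and the data are meant for registration (Protocol 4.5). Whether response declines is an open question. In the two earlier phase 3 trials, the week-4 composite rates of at least 1 point improvement after the first, second and third re-treatment were 81.5%, 74.4% and 70.3% (BLESS I) and 82.4%, 78.9% and 71.1% (BLESS II). A small p-value in each cycle could be read as maintained efficacy when it shows only that some subjects responded again. No comparison with cycle-1 week-4 response is planned.

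**Working it through.** **The plan's own figures.** The documents give no figure for the McNemar test. The figures used here do reproduce. Fisher's exact test with 39 and 13 subjects, 46% against 2%, one-sided 0.025, has power 92.27% by exact enumeration (92.3% stated, SAP 5). Enrolment of 353 x 0.85 = 300 completers, and 300 x 0.75 = 225 on active.

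**Step 1: response at the End of Cycle visit.** Both ratings are 2 or 3.
- Measured from that visit, as endpoint 11 requires, the change is 0.
- Measured from day 0, where the score is at most 3, the improvement is at most 3 - 2 = 1 point, and a score of 0 or 1 is not reached.

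Response is therefore 0% under either reference. The exception is a breach of the visit rules, such as re-treatment without meeting all criteria, which SAP 6.6 lists as a deviation.

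**Step 2: the test with that margin at zero.** Let b be the number responding at week 4 only, and c the number responding at End of Cycle only, so c = 0. Uncorrected chi-square = (b - c)²/(b + c) = b. Continuity-corrected = (b - 1)²/b. Exact two-sided p = 2 x 0.5^b. The cycle size does not enter, and the SAP does not say which form applies.

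| b | uncorrected p | corrected p | exact p |
|---|---|---|---|
| 3 | 0.083 | 0.248 | 0.250 |
| 4 | 0.0455 | 0.134 | 0.125 |
| 5 | 0.025 | 0.074 | 0.0625 |
| 6 | 0.014 | 0.041 | 0.031 |

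The threshold is 4 responders (uncorrected) or 6 (exact or corrected).

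**Step 3: as a response rate.** The documents do not say how many subjects reach each cycle, so the sizes are assumptions: 4/225 to 6/225 = 1.8% to 2.7%; 4/100 to 6/100 = 4% to 6%; 4/50 to 6/50 = 8% to 12%.

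**Step 4: chance of significance.** This is P(X ≥ 6) to P(X ≥ 4), with X binomial (n, true week-4 rate).

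| True rate | n = 50 | n = 100 | n = 225 |
|---|---|---|---|
| 46% | >99.9% | >99.9% | >99.9% |
| 23% | 98-99.9% | >99.9% | >99.9% |
| 10% | 38-75% | 94-99% | >99.9% |
| 5% | 4-24% | 38-74% | 97-99.7% |
| 2% | 0-2% | 1.5-14% | 30-66% |
| 0% | 0% | 0% | 0% |

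The test separates almost no responders from a few responders. It cannot separate 46% from 23%.

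**Step 5: the two-arm listing.** In cycles 2 to 4 every subject receives BoNT/A-DP. For endpoint 11, excluding placebo-first subjects leaves one randomized group, so a two-arm CMH test cannot be computed. Endpoint 13 is defined in the BoNT/A-DP group only. The section also confines every endpoint except response 4 weeks after re-treatment to the first cycle, and endpoint 13 has no first-cycle data.

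**Step 6: what a paired comparison with cycle 1 could deliver.** Let p10 and p01 be the two discordant proportions and d the difference in rates. The 95% half-width is 1.96 x sqrt((p10 + p01 - d²)/n). With n = 150 and 46% in both cycles:
- within-subject correlation 0: p10 = p01 = 0.46 - 0.46² = 0.2484, half-width 11.3 points;
- correlation 0.5: p10 = p01 = 0.1242, half-width 8.0 points.

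Power against a fall from 46% to 23% is about 99% or more. The n and the correlations are assumptions.

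**The case against.** The strongest reply is that this is one exploratory p-value beside usable estimates. No alpha, primary test or key secondary test depends on it. The stated objective is to assess the proportion of responders after each treatment, and the per-cycle proportions, with intervals where appropriate, can describe maintenance whatever the McNemar result. No passage says the test is meant to show maintained efficacy. All of this stands and limits the severity.

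A reader might infer that the test is significant whatever the drug does, or that it says nothing about re-treatment. The documents support neither. At 0%, the week-4 placebo result in BLESS I, it is never significant. At 2%, the placebo rate assumed in SAP 5, it is significant 30-66% of the time with 225 subjects and at most 14% with 100. It does ask whether any appreciable response returns, which is a low bar but not an empty one.

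The two-arm listing can be defended as loose drafting, since endpoint 11 receives its own rule a few lines later. That is fair: it biases no result. Taken literally, though, it cannot be programmed.

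A comparison with cycle 1 also has a trap. Cycle 1 is scored from the day-0 baseline, and endpoint 11 from the End of Cycle rating. A subject rated 3 at day 0, 2 at End of Cycle, and 1 at week 4 of both cycles is a responder in cycle 1 but not after re-treatment. An apparent loss could come from the change of reference alone, so a common definition is needed.

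**Conclusion.** Wrong as written; moderate, because the analysis is exploratory. Response at the comparison visit is zero by design apart from deviations, and 4 to 6 responders give two-sided p<0.05 at any cycle size. These two statements follow from the documents and the test formulae alone.

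The percentages and probabilities rest on assumed cycle sizes of 50 to 225, and on carrying the 46% planning rate for cycle 1 over to re-treatment. Over that range the test is at least 98% likely to be significant even if the rate is halved. It therefore gives no evidence on whether efficacy is maintained from cycle to cycle. It does not follow that efficacy after re-treatment goes unreported, or that any confirmatory conclusion is at risk.

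**What to change.** In SAP 8.1 and 8.6.4:
- Delete the McNemar test against the End of Cycle visit.
- Remove endpoints 11 and 13 from the CMH and chi-square list, and exempt endpoint 13 from the first-cycle-only sentence.
- For each open-label cycle, report the week-4 responder proportion with a Wilson 95% CI, without the where-appropriate qualifier.
- In BoNT/A-DP-first subjects, add an exploratory within-subject difference, with 95% CI, between cycle-k and cycle-1 week-4 response. Use one definition in both cycles, for example FWS 0 or 1 by both raters with at least 2 points improvement from the original day-0 baseline.

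Record the departure from Protocol 12.4.2 in SAP section 9. The report should state two limits of the paired comparison: cycle 1 is blinded and later cycles are open label, and subjects who reach later cycles are selected by earlier relapse.

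The cost is SAP wording and one replaced table. The ratings are already scheduled at baseline and at week 4 of every cycle.

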8.7 Safety Analyses

This section describes the safety analyses that will be conducted on the double blind and the open label treatment period, i.e., the safety analyses on all data collected during these treatment periods and all data collected in subjects who dropped-out during one of the treatment periods.

All definitions relative to safety endpoints are detailed in the following sections.

Safety analyses will be conducted on the SAF population and will be performed for all safety variables specified below.

All safety data will be summarized by treatment group.

The safety analyses of changes from baseline to a specific time point in safety variables (e.g., laboratory parameters, vital signs, and ECG) will only include subjects from the SAF population who have data available for both the baseline and the time point under consideration unless otherwise specified.

No statistical testing methods will be applied to statistically evaluate the differences on safety variables between treatment groups. Safety endpoint variables will be analyzed descriptively only.

An additional safety evaluation will be performed for laboratory data, vital signs, and ECG by defining cycle 2 day 0 as baseline (or last available value before drug administration of Cycle 2) for all subjects.

8.7.1 Treatment Exposure

A summary table displaying the number of subjects by the number of treatment cycles will be prepared. The duration of study drug exposure (calculated as described in Section 8.5.1) during each treatment cycle will be analyzed by summary statistics.

8.7.2 Adverse Events

All AEs will be classified by SOC and PT according to MedDRA Version 22.0 or higher.

In summaries by SOC and PT, adverse events will be sorted by decreasing frequency within each SOC and PT. In summaries by PT, AEs will be sorted by decreasing frequency within each PT.

AE summary tables will be presented for TEAEs and AESIs separately by treatment cycle and will include the number and percentage of subjects with any:

- TEAE/AESI

Statistical Analysis Plan (SAP)

CROMA
est. 1976

- TEAE/AESI related to study medication (AE will be defined as related if causality is definitely, probably or possibly or if causality assessment is missing)
- TEAE/AESI related to injection procedure (AE will be defined as related if causality is definitely, probably or possibly or if causality assessment is missing)
- Severe TEAE/AESI
- Severe TEAE/AESI related to study medication
- Severe TEAE/AESI related to injection procedure
- TEAE/AESI leading to discontinuation
- Study medication related TEAE/AESI leading to discontinuation
- Serious TEAE/AESI
- TEAE/AESI leading to death.

[figure not shown]
All TEAEs as well as all AESIs will be summarized by SOC, PT and treatment group using frequency counts and percentages (i.e., number and percentage of subjects with an event).

The number of events, as well as the number and rate of affected subjects will be reported by SOC and PT for all TEAEs and for all AESIs separately.

Adverse events will be separated to pre-treatment AEs and TEAEs. TEAEs are defined as all AEs with onset or worsening (increase in severity) after receiving first dose of study medication (independent of whether it is BoNT/A-DP or placebo). If it cannot be determined whether an AE is treatment-emergent due to missing onset cycle or a partial onset date, then it will be counted as treatment-emergent.

TEAEs and AESIs will be analyzed overall (for BoNT/A-DP or placebo), and for BoNT/A-DP treatment group additionally separately per first treatment cycle or open label extension phase: events starting on or after first treatment up to before open label extension (first cycle), and events starting on or after re-treatment until end of study (open label phase). If it cannot be determined whether an AE started during the first treatment cycle or the open label extension phase due to missing onset cycle and a partial onset date, then it will be counted as having started during the first treatment cycle. The cycle of onset as recorded in the eCRFs will be used for reported AEs by cycle where appropriate.

Events of subjects who started the first treatment with placebo but then entered the open label extension for re-treatment with BoNT/A-DP will be considered to placebo for the first cycle and to BoNT/A-DP for the open label phase.

Statistical Analysis Plan (SAP)

CROMA
est. 1976

TEAEs and AESIs (per SOC and PT) will also be summarized by seriousness, severity, relationship to study medication, and relationship to procedure using frequency counts and percentages (i.e., number and percentage of subjects with an event).

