Besides the FAS population for the analysis with multiplicity control, the analyses of these endpoints will also be based on the MFAS and the PP population. For all analyses, a one-sided significance level of 0.025 will be used, if not stated otherwise. Additional exploratory subgroup analyses by site, or by subjects with previous use of botulinum toxin versus naïve subjects, will be conducted for additional secondary analyses. For secondary endpoint 4 all subgroup analyses as described for the primary endpoint will be conducted. For the proportion of subjects with \geq 1 point reduction in FWS score during the first treatment cycle at week 12, 16 and 20 relative to baseline subgroup analyses by site, by country, by geographic region and by subjects with previous use of botulinum toxin versus naïve subjects will be conducted.

Secondary Safety Endpoints:

No statistical testing methods will be applied to statistically evaluate the differences on safety variables between treatment groups. Safety endpoint variables will be analyzed descriptively only.

Analysis of secondary safety endpoint 1 (adverse events):

Adverse events will be separated to pre-treatment AEs and TEAEs. TEAEs are defined as all AEs with onset or worsening (increase in severity) after receiving first dose of study medication (independent of whether it is BoNT/A-DP or placebo). If it cannot be determined whether an AE is treatment-emergent due to a partial onset date, then it will be counted as such.

TEAEs will be analyzed overall (for BoNT/A-DP or placebo), and for BoNT/A-DP treatment group additionally separately per first treatment cycle or open label extension phase: events starting on or after first treatment up to before open label extension (first cycle), and events starting on or after re-treatment until end of study (open label phase). If it cannot be determined whether an AE started during the first treatment cycle or the open label extension phase due to a partial onset date, then it will be counted as having started during first treatment cycle.

Events of subjects who started the first treatment with placebo but then entered the open label extension for re-treatment with BoNT/A-DP will be considered to placebo for the first cycle and to BoNT/A-DP for the open label phase.

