3.3 Study Treatments and Assessments

Subjects will participate in this study for a duration of 50 to 62 weeks from signing the informed consent form (ICF) to the End of Study visit (i.e., up to 14 calendar days for screening, followed by 48 to 60 weeks study participation).

Subjects will receive a maximum of four permitted rounds of treatment, with a minimum interval between treatments of 12 weeks.

The first treatment cycle of the study will comprise of two treatment groups as follows:

- Group A (active): BoNT/A-DP (20 units, 0.5 mL).
- Group B (placebo control): sterile, 0.9% sodium chloride (0.5 mL).

An interim analysis (IA) will be performed when all subjects complete the re-evaluation for retreatment visit at week 16 of the first treatment cycle or complete the double blind phase (whichever occurs earlier). Refer to Section 8.9 for more details regarding the IA.

Eligible subjects will be randomized at baseline (day 0) to Group A or B to receive the first treatment in a 3:1 randomization scheme, respectively. Investigators and subjects will be blinded to the treatment administered and will evaluate the severity of glabellar lines independently. The subjects must perform their assessment independently and ideally before the investigator, to ensure they are not biased by the investigator. The same investigator must assess the subject at baseline and at the visits at weeks 1, 2 and 4 in the first treatment cycle.

After a screening period of up to 14 calendar days, subjects will receive the first treatment (BoNT/A-DP or placebo) and attend for visits at 1, 2 and 4 weeks after treatment and at 4-

Statistical Analysis Plan (SAP)

CROMA
est. 1976

weekly intervals thereafter for evaluation of efficacy and safety (primary and key secondary efficacy endpoints will only be evaluated in the first treatment cycle in comparison with placebo). Re-screening will not be permitted.

The effect of botulinum toxin typically lasts a few months, hence the first treatment cycle will last at least 12 weeks and will end when the subjects qualify for re-treatment.

Open Label Extension

After the first treatment cycle is completed, all subjects may enter the open label extension phase and will be dosed with BoNT/A-DP (20 U) for subsequent re-treatments.

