7.2.2 Handling of Missing or Incomplete Dates

7.2.2.1 Imputation Rules for Missing or Partial AE Start Date:

If the cycle of onset is missing, the following rules will be applied.

If only Day of AE start date is missing:

If the AE start year and month are the same as that for the first dose date, then:

- If the full (or partial) AE end date is NOT before the first dose date or AE end date is missing, then impute the AE start day as the day of first dose date.
- Otherwise, impute the AE start day as 1.

Statistical Analysis Plan (SAP)

CROMA
est. 1976

Otherwise, if the AE start year and month are not the same as that for the first dose date, then impute the AE start day as 1.

Compare the imputed AE start date with the first dose date to determine whether the AE is pre-treatment AE or treatment emergent adverse event (TEAE).

If only Day and Month of AE start date are missing:

If AE start year = first dose year, then:

- If the full (or partial) AE end date is NOT before the first dose date or AE end date is missing, then impute the AE start Month and Day as the Month and Day of first dose date;
- Otherwise, impute the AE start Month as January and the AE start Day as 1.

Otherwise, if AE start year not equal first dose year, then impute the AE start Month as January and the AE start Day as 1.

Compare the imputed AE start date with the first dose date to determine whether the AE is pre-treatment AE or TEAE.

If Year of AE start date is missing:

If the year of AE start is missing or AE start date is completely missing then query site with no imputation. Also compare the full (or partial) AE end date to the first dose date. If the AE end date is before the first dose date then the AE should be considered as a pre-treatment AE. Otherwise, the AE will be considered as TEAE.

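### Double-blind adverse-event percentages compare arms over unequal, effect-dependent follow-up, with no common time window or exposure-adjusted rate

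*SAP*

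**What the plan says.** **Length of cycle 1.** SAP 3.3 states that "the first treatment cycle will last at least 12 weeks and will end when the subjects qualify for re-treatment". SAP 3.1 adds that cycles extend in four-week steps according to treatment effect. Protocol 7.3 sets the trigger for re-treatment: a score of 2 or 3 at maximum frown by both the investigator and the subject.

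**How adverse events are tabulated.** SAP 8.7.2: "AE summary tables will be presented for TEAEs and AESIs separately by treatment cycle and will include the number and percentage of subjects with any" of a list of event types. The tables by system organ class and preferred term give numbers of events and numbers and percentages of subjects. Exposure is summarised separately, by group and phase in 8.5.1 and by cycle in 8.7.1. It is not used as a denominator for adverse events. No fixed window is defined.

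**Interim and final tables.** SAP 8.9 cuts the interim tables at the week-16 visit. It then repeats the safety tables at the final analysis with both phases included.

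**Events of unknown phase.** Under SAP 8.7.2, an event that cannot be placed in cycle 1 or the open-label phase "due to missing onset cycle and a partial onset date, then it will be counted as having started during the first treatment cycle". Events of placebo-first subjects "will be considered to placebo for the first cycle and to BoNT/A-DP for the open label phase". The default source is the case report form: "The cycle of onset as recorded in the eCRFs will be used for reported AEs by cycle where appropriate". Protocol 12.4.2 has the same default, triggered by the partial date alone: "due to a partial onset date, then it will be counted as having started during first treatment cycle".

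**The concern.** The double-blind phase is the only randomised safety comparison in the trial, and an adequate safety database is both a stated objective and a stated reason for the sample size. A placebo subject whose lines never improve qualifies for re-treatment at week 12 and leaves cycle 1. An active subject who still has benefit stays on and continues to accrue background events such as colds and headaches. A crude percentage counts those extra weeks as if they were a drug effect, and a reader of the table cannot separate the two.

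The unknown-phase rule raises a smaller question. An event that may have followed open-label BoNT/A-DP in a placebo-first subject is reported under a treatment the subject may no longer have been on. That matters only for rare events, where one subject can change the picture.

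**Working it through.** The plan gives no expected cycle-1 length beyond the 12-week minimum and no expected adverse-event rate, so there is no stated figure to reproduce. The check uses the earlier trials described in the protocol.

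**Inputs.** Composite rates of at least 1-point improvement at maximum frown, from Protocol 4.4.2.1 and 4.4.2.2:

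| | Week 12 | Week 16 | Week 20 |
|---|---|---|---|
| BLESS I active | 45.1% | 20.8% | 9.9% |
| BLESS I placebo | 1.2% | 0.6% | 0.0% |
| BLESS II active | 40.5% | 12.1% | 4.7% |
| BLESS II placebo | 2.1% | 0.0% | 0.0% |

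**Assumption 1.** These rates stand in for the share of subjects still in cycle 1 after each visit.

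**Step 1: mean cycle-1 length in weeks** = 12 + 4 × (S12 + S16 + S20), ignoring time beyond week 24.

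- BLESS I: active 12 + 4 × 0.758 = 15.03; placebo 12 + 4 × 0.018 = 12.07; ratio 1.245.
- BLESS II: active 12 + 4 × 0.573 = 14.29; placebo 12 + 4 × 0.021 = 12.08; ratio 1.183.

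**Step 2: interim tables, cut at week 16** = 12 + 4 × S12.

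- BLESS I: 13.80 against 12.05; ratio 1.146.
- BLESS II: 13.62 against 12.08; ratio 1.127.

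**Step 3: apparent excess when the true event rates are equal.** **Assumption 2** is a constant hazard, the same in both arms: p(active) = 1 − (1 − p(placebo))^ratio.

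| Placebo incidence | Active, full cycle 1 | Excess (points) | Active, week-16 cut | Excess (points) |
|---|---|---|---|---|
| 2.3% (related events on placebo, BLESS I) | 2.7-2.9% | 0.4-0.6 | about 2.6% | 0.3 |
| 10% (assumed) | 11.7-12.3% | 1.7-2.3 | 11.2-11.4% | 1.2-1.4 |
| 30% (assumed) | 34.4-35.9% | 4.4-5.9 | 33.1-33.5% | 3.1-3.5 |

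**Step 4: unknown-phase rule.** At 3:1, 353 subjects split into about 265 active and 88 placebo. One subject added to the placebo column is 1/88 = 1.1 points. For scale, the related-event difference in BLESS I was 3.6% − 2.3% = 1.3 points. The likely count is small. If 20-40% of subjects have an open-label event and 1-5% of those events have unknown phase (both assumed), the number of placebo-first subjects affected lies between 88 × 0.20 × 0.01 = 0.2 and 88 × 0.40 × 0.05 = 1.8.

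**The case against.** **The imbalance will be visible.** Exposure is tabulated by group and phase, event counts are reported, and safety is descriptive with no testing. A careful reader could form approximate event rates. This limits the harm. It does not provide a like-for-like percentage of subjects with an event, which is the figure usually carried forward.

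**The size rests on a proxy.** This stands. A subject who improves from 3 to 2 counts as improved in the proxy but qualifies for re-treatment; a subject whom only one rater scores below 2 does not qualify. The true lengths could therefore lie on either side, and 15 weeks is not a lower bound. The documents do not give the denominators for the week-16 and week-20 rates. The 2020 hold on re-treatment may have lengthened cycle 1 by an unknown amount. A constant hazard overstates the excess for events that cluster soon after injection.

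**A reader might expect a spurious excess of 5 or 6 points.** That needs a 30% incidence, for which the documents give no source, together with full cycle-1 follow-up. At the BLESS I related-event rate on placebo the excess is about half a point.

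**A reader might infer that the unknown-phase rule biases the randomised comparison in favour of the drug.** The documents do not support that. The SAP rule needs both a missing onset cycle and a partial date, and otherwise the recorded cycle is used. It also moves unknown-phase events of active-first subjects into cycle 1, so the cycle-1 difference changes little. Only the treatment label is doubtful, and only for placebo-first subjects.

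**The date rule might look like a second route to the same error.** Under SAP 7.2.2.1, where only the day is unknown and the event falls outside the month of first treatment, the instruction is "then impute the AE start day as 1". Such a date would usually precede a re-treatment later in that month. But these rules apply only when the onset cycle is missing, and their stated use is to separate pre-treatment from treatment-emergent events. Section 8.7.2 has its own rule for phase.

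**Conclusion.** The main point holds. Double-blind follow-up depends on treatment effect by design, and the plan compares crude percentages over it without a common window or an exposure-adjusted rate. Under the stated proxy, active subjects have roughly 18-25% more cycle-1 follow-up in the final tables and 13-15% more in the interim tables. With equal constant hazards the resulting active excess is about 0.5 points at 2.3% incidence, 2 points at 10%, and 4.5 to 6 points at an assumed 30%. It runs against the test drug.

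The unknown-phase rule is a separate, minor matter that runs the other way for placebo-first subjects. The two act on different events, so they should not be assumed to cancel, and they do not add up to one distortion of known sign. The change is worth making because it is cheap and concerns the only controlled safety contrast. It has no bearing on the efficacy conclusions.

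**What to change.** 1. **SAP 8.7.2 and 8.9:** base the controlled comparison on treatment-emergent events and events of special interest with onset in study days 1-84 in both arms. By the SAP's own day count the week-12 visit is day 85, so this window closes before the earliest permitted re-treatment. State how partial dates enter the window, with one rule for both arms.
2. **SAP 8.7.2:** add exposure-adjusted incidence rates for the full double-blind phase. Person-time should run from first dose to re-treatment or, if there is none, to the last visit, so that it matches the period over which cycle-1 events are counted, including any delay from the 2020 hold.
3. **Unknown-phase events:** keep the existing rule for the cycle-1 contrast. Moving only the placebo-first events out of cycle 1 would make allocation depend on arm. Add a sensitivity listing or small table that counts such events in placebo-first subjects under open-label BoNT/A-DP.

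The cost is some SAP wording and a few extra tables from data already collected. Trial conduct and the efficacy analyses do not change. Because the unknown-phase rule itself is retained, the plan stays in line with Protocol 12.4.2 on that point.
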